#### **10.1.2.2 Psoriasis Efficacy Analysis Set**

The psoriasis efficacy analysis set will consist of all randomized subjects with baseline BSA  $\geq 3\%$ . Analyses of psoriasis efficacy endpoints (eg, sPGA, BSA) will be based on the psoriasis efficacy analysis set.

#### **10.1.2.3 Safety Analysis Set**

The safety analysis set will consist of all randomized subjects who receive at least one dose of investigational product. Subjects will be analyzed according to the actual treatment received. Analyses of safety endpoints will be based on the safety analysis set.

#### **10.1.3 Covariates and Subgroups**

The following covariates will be considered to assess their influence on the primary and key secondary endpoints:

- Age ( $\leq 65$ ,  $> 65$ )
- Sex (male, female)
- Race (Caucasian, Non-Caucasian)
- Ethnicity (Hispanic or Latino vs Non-Hispanic or Latino)
- Baseline body mass index (BMI) ( $\leq 30$ ,  $> 30$ )
- Baseline weight ( $\leq 100$  kg,  $> 100$  kg)
- Baseline BSA ( $\leq 3\%$ ,  $> 3\%$ )
- Prior use of non-biologic DMARD (yes, no)
- Disease duration ( $\leq$  median,  $>$  median)

Subgroup analyses, which would be considered exploratory, may be performed if an examination of the above covariates suggests that any treatment difference for the primary and secondary endpoints depends on any baseline covariates.

#### **10.2 Sample Size Considerations**

A total of 840 subjects will be enrolled in the study and randomized in a 1:1:1 ratio to etanercept plus methotrexate therapy, etanercept monotherapy and methotrexate monotherapy.

To preserve the family-wise 2-sided type one error rate at 0.05 for the multiple comparisons of the etanercept plus methotrexate therapy and etanercept monotherapy groups with methotrexate monotherapy, a Bonferroni-based gatekeeping chain procedure ([Burman et al, 2009](#) and [Millen et al, 2011](#)) will be used to determine statistical significance for the primary and key secondary endpoints as described in

[Section 10.5.2](#). This procedure will split alpha of 0.05 equally to test in parallel the primary and key secondary endpoints (ACR 20, MDA) for etanercept plus methotrexate therapy vs. methotrexate monotherapy and etanercept monotherapy vs. methotrexate monotherapy sequentially within each parallel path. If one of the parallel paths rejects both hypotheses sequentially, and the other parallel path has at least one hypothesis not rejected, then unspent alpha of 0.025 from the successful path will be propagated to the hypotheses in the other path to re-test them sequentially at a level of 0.05.

The sample size is based on the adequacy to evaluate the efficacy of etanercept monotherapy compared with methotrexate monotherapy as measured by the primary endpoint of ACR 20 response at week 24 at a significance level of 0.025 based on the Bonferroni-based gatekeeping chain procedure.

There are no published studies of etanercept monotherapy versus methotrexate monotherapy for the treatment of PsA. Therefore for the purpose of this study the assumed response rates for ACR 20 for the etanercept monotherapy and methotrexate monotherapy arms are derived from separate studies. In the etanercept PsA pivotal phase 3 study (20021630 Study) the ACR 20 response rate at week 24 was 50% for the etanercept arm. However, subjects were allowed to be on a stable dose of methotrexate at study entry. Assuming a methotrexate naïve population would respond better, the response rate for the etanercept monotherapy arm in this planned phase 3 study is assumed to be 60%.

In a recent randomized placebo-controlled trial of methotrexate monotherapy in PsA ([Kingsley et al, 2012](#)) the ACR 20 response rate for the methotrexate monotherapy arm was 34%. However, the dose of methotrexate was 15 mg QW. Assuming a higher dose of methotrexate (ie, 20 mg QW) would yield better responses, the response rate for the methotrexate monotherapy arm in this planned phase 3 study is assumed to be 44%.

Therefore, in order to detect a difference of 16% between the etanercept monotherapy and methotrexate monotherapy arms, using a two-sided Chi-square test at a significance level of 0.025 and 90% marginal power, each treatment arm will have approximately 280 subjects adjusting for an anticipated 10% dropout.

This sample size will provide marginal power > 90% to detect a treatment difference in ACR 20 response at week 24 between the etanercept plus methotrexate therapy arm and the methotrexate monotherapy arm at a two-sided 0.025 significance level. As previously mentioned, the ACR response rate at week 24 is assumed to be 44% for the

methotrexate monotherapy arm. The ACR response rate at week 24 for the etanercept plus methotrexate therapy arm is assumed to be 5% higher than the etanercept monotherapy arm (ie, 65%). This is based on a longitudinal observational study assessing the role of TNF-inhibitor plus methotrexate combination therapy versus TNF-inhibitor monotherapy ([Fagerli et al, 2014](#)).

In addition, this sample size will provide marginal power > 90% to detect treatment differences in MDA response at week 24 between both etanercept arms and the methotrexate arm at a two-sided 0.025 significance level, assuming response rates of 15%, 30%, and 35% for the methotrexate monotherapy, etanercept monotherapy, and etanercept plus methotrexate therapy arms, respectively. In recent PsA trials, the MDA 24-week response rates for the placebo arm range from 3 to 7% ([Coates et al, 2010a](#); [Kavanaugh et al, 2013](#)). Therefore, for the methotrexate monotherapy arm, the response rate is assumed to be higher at 15%. In the pivotal phase 3 randomized placebo-controlled trial of etanercept in PsA, the MDA response rate for the etanercept monotherapy arm is estimated to be approximately 20% at week 24 (data on file). For a methotrexate naïve population, the response rate is assumed to be higher at 30%. In addition, the etanercept plus methotrexate therapy arm is assumed to have a 5% improvement over the etanercept monotherapy arm.

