## 2.4 Rationale

Etanercept has been approved for PsA by the FDA and Health Canada and is indicated for reducing the signs and symptoms, inhibiting the progression of structural damage of active arthritis, and improving physical function. Etanercept can be used in combination with methotrexate in patients who do not respond adequately to methotrexate alone.

Methotrexate is one of the most commonly used non-biologic DMARD in PsA as monotherapy or in combination therapy with other synthetic DMARDs or with biologic DMARDs. Although methotrexate is commonly used in treating PsA, it is unclear how effective it is in PsA. The most recent randomized placebo-controlled trial of methotrexate in PsA is the Methotrexate in Psoriatic Arthritis (MIPA) study ([Kingsley et al, 2012](#)). This was a 6-month, double-blind, parallel-group study in methotrexate naïve subjects randomized to receive methotrexate (15 mg/wk; n = 109) or placebo (n = 112). In an intent-to-treat analysis, there were no statistically significant improvements in measures of disease activity across groups at 24 weeks. The odds ratios (95% CI) for Psoriatic Arthritis Response Criteria, ACR 20, and Disease activity score (28 joint) responders for the methotrexate and placebo groups were 1.77 (0.97, 3.23; p = 0.06), 2.00 (0.65, 6.22; p = 0.23), and 1.70 (0.90, 3.17; p = 0.10), respectively. In a completer analysis, percent responders for methotrexate and placebo were 34% and 21% for ACR 20 respectively for a difference of 13%. In the PsA pivotal trial, ACR 20 response at week 24 was 50% and 14% in the etanercept and placebo groups respectively for a difference of 36%. Nevertheless, comparisons with the MIPA trial need to be qualified by the fact that the subjects in the etanercept pivotal trial were not uniformly methotrexate naïve. Furthermore, in the MIPA trial the target dose of methotrexate was 15 mg QW, a less than maximal clinically used dose level.

In rheumatoid arthritis, combining TNF inhibitors such as etanercept with methotrexate leads to superior efficacy relative to each agent used alone ([Klareskog et al, 2004](#)). The role of methotrexate in combination with etanercept in PsA remains unclear. Analysis of

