### **10.4 Planned Analyses**

#### **10.4.1 Primary Analysis**

The objective for the primary analysis is to evaluate the efficacy of etanercept plus methotrexate therapy and etanercept monotherapy compared to methotrexate monotherapy in subjects with PsA at week 24 as measured by the proportion of subjects achieving an ACR 20 response. The primary analysis will be performed when the last subject completes the week 48 visit or terminates early from the study, at which time the study will be unblinded.

For the primary and key secondary efficacy endpoints, treatment effect will be tested using a Bonferroni-based gatekeeping chain procedure ([Burman et al, 2009](#) and [Millen et al, 2011](#)) as described in Section 10.5.2 to control the family-wise 2-sided type one error rate at 0.05. Between-treatment comparisons will be made using the stratified Cochran-Mantel-Haenszel (CMH) test with baseline BMI and prior non-biologic DMARD use as the stratification factors. Missing data will be imputed using non-responder imputation for the primary analysis.

For other efficacy endpoints, the significance level will be 0.05 without adjusting for multiplicity and data will be analyzed as observed.

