In a recent randomized placebo-controlled trial of methotrexate monotherapy in PsA ([Kingsley et al, 2012](#)) the ACR 20 response rate for the methotrexate monotherapy arm was 34%. However, the dose of methotrexate was 15 mg QW. Assuming a higher dose of methotrexate (ie, 20 mg QW) would yield better responses, the response rate for the methotrexate monotherapy arm in this planned phase 3 study is assumed to be 44%.

Therefore, in order to detect a difference of 16% between the etanercept monotherapy and methotrexate monotherapy arms, using a two-sided Chi-square test at a significance level of 0.025 and 90% marginal power, each treatment arm will have approximately 280 subjects adjusting for an anticipated 10% dropout.

This sample size will provide marginal power > 90% to detect a treatment difference in ACR 20 response at week 24 between the etanercept plus methotrexate therapy arm and the methotrexate monotherapy arm at a two-sided 0.025 significance level. As previously mentioned, the ACR response rate at week 24 is assumed to be 44% for the methotrexate monotherapy arm. The ACR response rate at week 24 for the etanercept plus methotrexate therapy arm is assumed to be 5% higher than the etanercept monotherapy arm (ie, 65%). This is based on a longitudinal observational study assessing the role of TNF-inhibitor plus methotrexate combination therapy versus TNF-inhibitor monotherapy ([Fagerli et al, 2014](#)).

In addition, this sample size will provide marginal power > 90% to detect treatment differences in MDA response at week 24 between both etanercept arms and the methotrexate arm at a two-sided 0.025 significance level, assuming response rates of 15%, 30%, and 35% for the methotrexate monotherapy, etanercept monotherapy, and etanercept plus methotrexate therapy arms, respectively. In recent PsA trials, the MDA 24-week response rates for the placebo arm range from 3 to 7% (Coates et al, 2010a; Kavanaugh et al, 2013). Therefore, for the methotrexate monotherapy arm, the response rate is assumed to be higher at 15%. In the pivotal phase 3 randomized placebo-controlled trial of etanercept in PsA, the MDA response rate for the etanercept monotherapy arm is estimated to be approximately 20% at week 24 (data on file). For a methotrexate naïve population, the response rate is assumed to be higher at 30%. In addition, the etanercept plus methotrexate therapy arm is assumed to have a 5% improvement over the etanercept monotherapy arm.

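### The dropout inflation behind 280 per arm does not match non-responder imputation, so the stated 90% power depends on what the assumed rates of 60% and 44% mean

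*Protocol*

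**What the plan says.** Protocol 10.2 sizes the trial on etanercept monotherapy versus methotrexate monotherapy for ACR 20 at week 24. The inputs are:

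- Etanercept: "the response rate for the etanercept monotherapy arm in this planned phase 3 study is assumed to be 60" percent.
- Methotrexate: "methotrexate monotherapy arm in this planned phase 3 study is assumed to be 44" percent.
- Test: "using a two-sided Chi-square test at a significance level of 0.025 and 90% marginal power".
- Result: "90% marginal power, each treatment arm will have approximately 280 subjects adjusting for an anticipated 10% dropout".

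SAP 3.2 gives the same inputs and ends in the same place: "each treatment arm will have approximately 280 subjects adjusting for an anticipated 10% dropout".

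The analysis sections set a different rule for dropouts. The full analysis set is all randomized subjects (Protocol 10.1.2.1, SAP 7.1). Protocol 10.4.1 says: "Missing data will be imputed using non-responder imputation for the primary analysis". Protocol 10.5.2 and SAP 9.3.2 and 10.5.1 say the same for ACR 20 and MDA.

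On the source of the methotrexate assumption, Protocol 10.2 raises a published 34% to 44%. Protocol 2.4 says what kind of figure the 34% is: "In a completer analysis, percent responders for methotrexate and placebo were 34% and 21% for ACR 20 respectively". Neither document says what kind of rate the etanercept source figure of 50% is, or whether 60% and 44% already count dropouts as non-responders.

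**The concern.** Dividing by 0.9 is the right adjustment when dropouts leave the denominator and the remaining subjects show the full treatment difference. Under non-responder imputation (NRI) nobody leaves. Dropout lowers both response rates and shrinks the difference, while the number analysed stays at 280. The sizing and the primary analysis therefore use different models of dropout, and the 90% belongs to the first.

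This is the comparison that sets the trial size, and its ACR 20 test comes before the MDA test in the etanercept monotherapy path. Under NRI, power also depends on whether dropout is balanced between arms, which the calculation in the plan cannot show.

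**Working it through.** **Inputs (Protocol 10.2).** p1 = 0.60, p2 = 0.44, difference d = 0.16, mean rate p̄ = 0.52, two-sided alpha 0.025 (z = 2.2414), power 90% (z = 1.2816), 10% dropout.

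**Step 1: reproduce 280.**

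n = [2.2414 × √(2p̄(1−p̄)) + 1.2816 × √(p1(1−p1) + p2(1−p2))]² / d²

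= [2.2414 × 0.70654 + 1.2816 × 0.69742]² / 0.0256 = 239.8

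With the continuity correction: n′ = (n/4) × [1 + √(1 + 4/(n·d))]² = 252.1

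- Corrected: 252.1 / 0.9 = 280.1, the stated figure. Rounding up to 253 first gives 282, still approximately 280.
- Uncorrected: 239.8 / 0.9 = 266.4, which does not match.

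The stated design is therefore about 252 analysed subjects per arm at the full 16 points. Power at n = 252 is 90.0% corrected and 91.5% uncorrected.

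**Step 2: apply the planned rule.** With 10% missing in each arm and counted as failures:

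- Etanercept 0.60 × 0.9 = 0.540; methotrexate 0.44 × 0.9 = 0.396; difference 0.144; mean 0.468; n = 280.
- Standard error under the null: √(2 × 0.468 × 0.532 / 280) = 0.04217.
- Standard error under the alternative: √((0.540 × 0.460 + 0.396 × 0.604) / 280) = 0.04173.
- Uncorrected: (0.144 − 2.2414 × 0.04217) / 0.04173 = 1.186, power 88.2%.
- Corrected (difference reduced by 1/280): (0.14043 − 2.2414 × 0.04217) / 0.04173 = 1.100, power 86.4%.

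Exact binomial enumeration gives 88.1% and 86.4%.

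**Step 3: vary what the documents leave open** (n = 280 per arm, alpha 0.025).

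| Reading | Rates analysed | Power, corrected to uncorrected |
|---|---|---|
| Rates among subjects with data, 10% missing at week 24 | 54.0% vs 39.6% | 86.4% to 88.2% |
| Same, 7% missing | 55.8% vs 40.9% | 88.7% to 90.3% |
| Same, 5% missing | 57.0% vs 41.8% | 90.1% to 91.5% |
| Rates already NRI | 60% vs 44% | 93.1% to 94.2% |
| Only the methotrexate rate is a completer rate, 10% missing | 60% vs 39.6% | 99.5% to 99.6% |

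**Step 4: unequal dropout.** These splits are assumptions made for illustration; the documents give none.

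- 12% on etanercept, 8% on methotrexate: 52.8% vs 40.5%, power 72.6% to 75.4%.
- 8% on etanercept, 12% on methotrexate: 55.2% vs 38.7%, power 94.6% to 95.4%.

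**Step 5: the other powered comparisons,** each rate multiplied by 0.9.

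- Combination, ACR 20 (58.5% vs 39.6%): 98.6% to 98.8%.
- Etanercept monotherapy, MDA (27.0% vs 13.5%): 95.1% to 96.1%.
- Combination, MDA (31.5% vs 13.5%): about 99.8%.

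All stay above the stated 90%.

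**The case against.** The strongest reply is that the documents never establish the 54.0% versus 39.6% scenario.

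- **Kind of rate.** Protocol 10.2 presents 60% and 44% as the rates assumed for this trial, whose primary analysis is NRI. Read that way, 280 is conservative at 93% to 94%. The completer label is documented for the methotrexate source figure only, and both assumed rates are rounded uplifts from other trials. This stands as a limit on certainty. It does not explain why the sample size was inflated, because inflation has a purpose only if the rates apply to subjects who stay.
- **Timing.** The 10% is not dated, and treatment lasts 48 weeks. Subjects who stop treatment may continue assessments (Protocol 8.1). Those who leave are asked for an early termination visit (7.2.6), and the SAP week 24 window for joint counts runs from day 141 to day 210. Fewer than 10% may therefore lack a week 24 ACR 20. This stands: at 5% missing the stated power is met. Against it, the sizing applies the full 10% to a week 24 endpoint.
- **Continuity correction.** Neither document mentions one; it is inferred because it reproduces 280. Without it the shortfall is under 2 points. This stands, and is why a range is given.
- **Re-testing at 0.05.** Marginal power leaves out the second chance in the chain procedure. In the 10% scenario, simulation with a shared methotrexate arm, and with ACR 20 and MDA drawn independently (an assumption), gives about 91% to 92% probability of rejecting the etanercept monotherapy ACR 20 hypothesis. This stands as mitigation, but the figure the documents quote is marginal power at 0.025.

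A reader might infer that the trial is underpowered, that 280 is a calculation error, or that more subjects are needed. The documents support none of these. The 280 reproduces from its own inputs, and power falls below 90% only under conditions that the plan leaves unstated.

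**Conclusion.** The mismatch between sizing and analysis is real; its effect on power is conditional and modest. On the reading that the inflation step implies, marginal power for etanercept monotherapy versus methotrexate monotherapy on ACR 20 is about 86% to 88%, a shortfall of about 2 to 4 points against the stated 90%. That rests on three assumptions: 60% and 44% are rates among subjects with week 24 data, the full 10% is missing at week 24, and it is missing equally in both arms. If the first fails because both are already NRI rates, power exceeds 90%; if the second fails because only 5% is missing, power is at or just above 90%. The third matters most, since a modest imbalance moves power by more than the shortfall itself.

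It would go too far to state 86% to 88% as the trial's actual power. What can be said is that 90% was derived under a dropout model that the primary analysis does not use, and that the documents omit what is needed to replace it. Only this one powered comparison can fall below its stated level.

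**What to change.** Keep 280 per arm and leave the analysis unchanged. In Protocol 10.2 and SAP 3.2:

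1. State whether 60% and 44% are rates among subjects with week 24 data or rates with missing data counted as non-response.
2. State what proportion per arm is expected to lack a week 24 ACR 20 result.
3. Restate the marginal power for this comparison under NRI: about 86% to 88% for 54.0% versus 39.6% if the rates are among subjects with data and 10% is missing. If they are NRI rates, give about 93% to 94% and delete the dropout inflation. Say whether a continuity correction is used.
4. Optionally, add one line on unequal dropout, labelled as an assumption.

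The cost is wording in two sections and possibly a slightly less favourable stated power. No subjects are added and no test changes.

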### **10.3 Access to Individual Subject Treatment Assignments by Amgen or Designees**

Blinded individuals will not have access to unblinded information until the study is formally unblinded. Unblinding and potentially unblinding information should not be distributed to the study team, investigators or subjects prior to the study being formally unblinded (eg, the formal unblinding may occur at the final analysis rather than during the primary analysis) except as specified (eg, [Section 5.2](#), [Section 9.2.2](#) and Statistical Analysis Plan [SAP]).

### **10.4 Planned Analyses**

#### **10.4.1 Primary Analysis**

The objective for the primary analysis is to evaluate the efficacy of etanercept plus methotrexate therapy and etanercept monotherapy compared to methotrexate monotherapy in subjects with PsA at week 24 as measured by the proportion of subjects achieving an ACR 20 response. The primary analysis will be performed when the last subject completes the week 48 visit or terminates early from the study, at which time the study will be unblinded.

For the primary and key secondary efficacy endpoints, treatment effect will be tested using a Bonferroni-based gatekeeping chain procedure ([Burman et al, 2009](#) and [Millen et al, 2011](#)) as described in Section 10.5.2 to control the family-wise 2-sided type one error rate at 0.05. Between-treatment comparisons will be made using the stratified Cochran-Mantel-Haenszel (CMH) test with baseline BMI and prior non-biologic DMARD use as the stratification factors. Missing data will be imputed using non-responder imputation for the primary analysis.

For other efficacy endpoints, the significance level will be 0.05 without adjusting for multiplicity and data will be analyzed as observed.

## **10.5 Planned Methods of Analysis**

### **10.5.1 General Considerations**

Subject disposition, demographics, and baseline disease characteristics will be summarized descriptively by randomized treatment group.

For categorical endpoints, the descriptive statistics will contain the frequency and percentage. For continuous endpoints, the descriptive statistics will include the number of observations, mean, standard error, standard deviation, median, minimum, and maximum.

Treatment effect will be tested for the primary and key secondary endpoints using a Bonferroni-based gatekeeping chain procedure to control the family-wise 2-sided type one error rate at 0.05. The significance level for the analyses of other secondary endpoints and exploratory endpoints will be 0.05 without adjusting for multiplicity and the p-values for these endpoints will therefore be treated as a descriptive statistic only.

Safety endpoints will be tabulated by actual treatment received during the study. No formal statistical testing will be performed for safety analyses.

Details of all statistical methods will be provided in the SAP.

[figure not shown]
### **10.5.2 Primary and Key Secondary Efficacy Endpoints**

The primary analysis for the primary endpoint and key secondary endpoints, ACR 20 response and MDA response at week 24, will be performed using the full analysis set. Treatment effect will be tested using the stratified CMH test with baseline BMI and prior non-biologic DMARD use as the stratification factors.

[figure not shown]
To control the family-wise 2-sided type one error rate at 0.05 for the multiple comparisons of the etanercept plus methotrexate therapy and etanercept monotherapy

groups with methotrexate monotherapy across the primary and key secondary endpoints, the hypotheses will be tested using a Bonferroni-based gatekeeping chain procedure (Burman et al, 2009 and Millen et al, 2011) as shown in Figure 1. This procedure will split alpha of 0.05 equally to test in parallel the primary and key secondary endpoints (ACR 20, MDA) for etanercept plus methotrexate therapy vs. methotrexate monotherapy and etanercept monotherapy vs. methotrexate monotherapy sequentially within each parallel path. If one of the parallel paths rejects both hypotheses sequentially, and the other parallel path has at least one hypothesis not rejected, then unspent alpha of 0.025 from the successful path will be propagated to the hypotheses in the other path to re-test them sequentially at a level of 0.05. For example, suppose the nominal p-values for hypotheses A1, B1, A2, and B2 (Figure 1) are 0.01, 0.02, 0.03, and 0.055, respectively. In the first round of testing, hypotheses A1 and B1 are rejected, whereas hypotheses A2 and B2 are not rejected. However, since both hypotheses A1 and B1 are rejected, the procedure gives a second chance to re-test hypotheses A2 and B2 (according to the left arm of the figure) at a lower threshold of 0.05 rather than the original threshold of 0.025. Note that in this example A2 is rejected and hypothesis B2 is not rejected.

Figure 1. Bonferroni-based Gatekeeping Chain Procedure

ETN: Etanercept; MTX: Methotrexate

For the primary analysis of the primary and key secondary endpoints, missing data will be imputed as nonresponder. Sensitivity analyses using observed data and using last observation carried forward imputation will also be performed.

